5. Evaluation (How to determine what worked?). As part of our evaluation of our dissemination efforts, Golin will provide annual recap reports, ad hoc reports for media announcements, as well as a major ad-hoc launch report 30 days after the announcement of the major findings (e.g., Tallahassee event). The reports will capture:

- News, digital and social media coverage analysis including impressions, reach, and message pull through. Golin will collect news coverage data and provide details about impressions and reach. Our team will then review each story and count the number of campaign messages that appear in the stories and where it appears to adopt messages with high reach and coverage.
- Partner mobilization analysis including engagement and action by partners. Using appropriate tools (e.g. Facebook, Twitter ads, YouTube), Golin will identify posts by partners and report back those that have used campaign assets for more targeted messaging and partner mobilization.

Golin will also provide key performance indicators (KPIs) to the investigators for evaluation. These KPIs include impressions and reach of materials, engagement with social media content, number of people who have shared content online, social conversations, the number of times video/images have been viewed, and the number of times people have visited a campaign website after seeing/receiving campaign materials. To provide a benchmark for comparison, we will use KPIs from two recent campaigns conducted by Golin (e.g. Tobacco Free Florida Week eEpidemic and/or the Florida Clean Indoor Air Act vaping ban) (Tobacco Free Florida 2015).

In addition, Truth Initiative will use the messages and images we developed in their counter-tobacco campaigns, and evaluate them for further message development and fine-tuning. Truth Initiative has standard and extensive evaluation process for their campaigns (e.g. [name] et al., 2017; Hair et al., 2017). This process briefly involves three types of studies: Formative, Implementation and Outcome. Findings are continuously used to inform the process so that changes can be made in real-time help ensure campaign success (e.g. Hair et al., 2018).

6. Work plan. Timing of various publications will dictate the release tactics, but generally, important announcements will be supported with a rigorous public relations launch and an engagement strategy that activates partners. When releasing scientific data, it is important to include timeliness of the news (through a media event), and a hook to current events. This process will be timed and repeated ahead of major policy pushes at all stages of the proposed project and will be supplemented with various related activities.

Impact. As we have adopted a complementary approach for the development and testing of HWLs, each Aim feeds into the other, while also serving as a standalone study that will facilitate timely communication of our research findings to a variety of researchers, stakeholders, and policymakers involved in tobacco control in Florida. For example, the HWLs arising from our focus groups study (Aim 1) can be used by other researchers for further development and testing, while their messages and pictorials can be used within campaigns to increase young people in Florida awareness about the harms of WP smoking. Thus throughout the project we will produce and distribute toolkits, messaging, template social media assets, newsletters, and more (Table 2).

C.7. Potential challenges and their solutions

Long term effects of HWLs on smoking behavior is an important parameter that is rarely addressed in the HWLs literature (Noar 2016, a). However, given the complexity and limited portability of WP compared to cigarette pack, which complicates the assessment of HWLs on

smokers' behavior prospectively, we opted to study the effect of HWLs on smokers' behavior in a lab model (Aim 2). Thus, our proposed lab study provides a reliable method of gauging HWLs' short-term potential on WP smokers in the form they will be delivered in the real world.

Importantly, our planned short-term outcomes (e.g. reaction, harm perception, quit intention) have been shown to be strongly correlated with long terms outcomes of cessation (Borland 2009, Fathelrahman 2009, Li 2012). Still, to gauge the potential of HWLs, we have now added a 3-month follow-up assessment to evaluate longer-term recall, social interactions, and behavioral adaptations as a result of exposure to the HWLs (e.g., quitting and quit intention)(Brewer 2016).

D. STUDY TIMELINE

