Objectives and Hypotheses. To assess WP smokers' responses to the developed pictorial HWLs and inform the state of Florida about HWLs potential to curb WP use among youth in Florida. The study will examine smokers' harm perception, intention to quit, puff topography, satisfaction, dependence, and toxicants exposure (CO, nicotine, EBC oxidative stress) pre-post smoking under 2 conditions (H WL vs. no-H WL). We hypothesize that 1) HWLs on the device will reduce smoking (puffing) intensity, satisfaction, exposure to toxicants, dependence parameters and increase harm perception and intention to quit compared to no-HWL control; and 2) this effect will be more pronounced in beginning vs. established WP smokers.

Participants, Recruitment, and Procedures. As in Aim 1, in this study we will recruit WP smokers through the same online, offline and in-person recruitment methods described in section (C.2.2. Recruitment, Aim 1). Individuals who report smoking cigarettes or other tobacco/nicotine products (e.g., e-cigarettes, pipes, cigars) will be included to increase the generalizability of results, as long as they identify themselves as primarily WP tobacco smokers (do not report using cigarettes/e-cigarettes/other tobacco products regularly > 4 times/month). Concurrent regular use of other tobacco/nicotine products would bias the measurement of WP associated outcomes (e.g. dependence measures) (Ben Taleb 2018). *Participants completing the 2 lab sessions and 3-month follow-up will be compensated \$36 for each visit. Based on previous experience ([name] 2019, a), we expect to study 8-10 subjects/month. We will continue recruitment until we reach the target sample (248 with complete sessions). While recruitment is always a challenge, our lab, led by Co-PI [name] has easily recruited >150 WP users for two-session study (similar design) in the past 2 years with negligible drop out using comparable incentives ([name] 2019, a). This is due to the widespread of WP smoking among college students in Florida (up to 34%) (Martinasek 2016), especially in a large university with about 57,000 students such as FIU, where our lab is located.*

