to-medium effect size (Cohen's $f=0.19$) depending on HWL condition ([name] 2019, b). *This study will include 248 WP smokers (124 beginners; 124 established) randomized to 4 groups (62 each) along the 4 tested HWLs. Using repeated measures ANOVA F test with 2 within and 2 between factors, a total sample size of 240 participants will have at least 80% power to detect small-to-medium size effect (Cohen's $f=0.2$) or larger for $2 \times 2 \times 2 \times 4$ within-subject (H WL condition and time) and between-subject (smoking frequency and 4 different HWLs) effects, as well as their interactions at 0.05 level of significance, assuming sphericity and a moderate correlation (0.5) among repeated measures (Cohen 1988). The proposed sample size will provide sufficient power to detect small to medium effects expected based on our pilot data ([name] 2019, b). It is also feasible as we have not encountered any difficulty in recruiting a large number of WP smokers in our lab studies ([name] 2019, a).*

Screening, Informed Consent. Individuals who are identified as potentially eligible based on the phone screening will be asked to attend an onsite-screening, which will involve assessment of inclusion/exclusion criteria, physical examination, and urine pregnancy testing for women. Prior to screening, potential participants will undergo a review of the study and consent procedures to ensure that they understand the study, its risks/benefits, and their rights as research participants. Consented (written) individuals will then undergo a physical examination conducted by the research nurse, who will have access to an on-call Medical Monitor (physician) in case of concern or for consultation at any point of the study as it is the standard practice in our lab ([name] 2019, a, [name] 2019, b). The physical examination will include measuring BP, heart rate, temperature, pulse oximetry, and weight/height. Successfully consented/screened participants will be scheduled for their 1st session and asked to abstain from all tobacco use 12 hours prior to it.

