Experimental Methods. Participants will be randomly assigned to one of the 4 HWLs conditions and attend the lab for two, ~2-h sessions, separated by a 48-h washout period, and differ by HWL on the device (H WL vs. no-HWL control). Session order will be randomly counterbalanced to avoid order effects; counterbalancing also will allow us to study the effect of HWL on smoking behavior prospectively (i.e. between sessions difference is expected to be less when the HWL condition is tested first). They will also be balanced across the 4 HWLs (62 sessions for each HWL) to allow for equal numbers and robust comparisons of the 4 HWLs and their representative themes.

At the beginning of the 1st session, participants will provide demographic and personal information including age, socioeconomic status, race/ethnicity, and detailed tobacco use history, especially WP use. Then abstinence will be verified by eCO<5 ppm. Those who have eCO>5 ppm will be rescheduled. Those who are abstinent will get familiarized with the study procedures, measures, and they will be given time to adapt to the lab.

After adaptation, continuous measurement of physiological responses begins, and 10 ml of venous blood is sampled, and participants are asked to respond to subjective measures (pls. see below Outcome Measures). They will then begin a maximum 45 min WP smoking session (time recorded) using a device fitted with the pre-selected HWL or no-HWL according to condition. The HWL will be placed in a constant location/size on the device, which will be placed in front of participant seat (at vision level). For each participant, preferred brand/flavor of WP tobacco (verified at screening) will be used to neutralize the effect of nicotine/flavor on study outcomes. We will follow our tested lab protocol developed to study the WP (Ben Taleb 2018), where prior to each session, the lab staff will pack the WP head with 15 g of the participant's favorite tobacco preparation and cover it with perforated foil. Tobacco will be heated with quick-light charcoal disks (33 mm diameter; 6.2 g; Three Kings, Holland, or similar brand). Initially, a single charcoal disk will be used, and several (pre-weighed) ½ charcoal disks will be made available to the participants so they can add *ad libitum* (Cobb 2012). The timing of each

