Statistical Analysis. Prior to analysis, physiological data will be averaged to produce a single baseline value for each measure (10 minutes prior to WP use) and for each 10- minute that a participant was actually using the WP. Topography data will be processed automatically by the topography instrument software to eliminate closely spaced puffs (i.e., IPIs < 300 msec). Such puffs are assumed to be part of the previous puff and the recorded volume and duration values will be added to that preceding puff ([name] 2009). After this procedure, any puffs less than 5 ml will be considered an artifact and automatically discarded. Remaining data will be averaged for each participant in each condition using all remaining values for puff volume, duration, number, and IPI (Shihadeh 2004). We will address the issue of stability of WP puff topography by correlating topography values across sessions (Shihadeh 2005a). For plasma nicotine, values below the limit of quantitation (LOQ) will be replaced with the value of the LOQ ([name] 2011). Demographical data will be examined to determine if there are significant between-group differences on measures that may be related to study outcome (some differences are expected due to design such as past 30-day WP use) though these are expected to be minimized as a virtue of randomization. Unexpected between-group differences will be considered as potential adjustment covariates in the primary analysis (Evans 2006). *The primary analysis of each outcome will involve a 4-factor analysis of variance (or covariance) with two within-subject factors; HWL (HWL vs. no-HWL/control) and time (pre-post smoking), and two between-subject factors; smoking frequency (beginner vs. established WP smokers) and HWL (4 group assignment). This approach will be extended into mixed-effects linear regression model in order to adjust for potential confounders such as gender, education, race, SES, and self-efficacy. To assess if gender has any effect on the results, it will be considered as a covariate and we will test the pre-planned interaction with it to determine heterogeneity of HWL by gender as well as potential differential effects.* We will test for carry over effect statistically and will control for it when testing for the primary factors (Senn 2002). Significance levels will be adjusted for violations of the sphericity assumption using Huynh-Feldt corrections (Keppel 1991). The mean square error terms for the overall interaction will be used to conduct Tukey's honestly significant difference test (Keppel 1991), with comparisons at $P < 0.05$ considered significant.

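### One-session participants are in effect left out of the primary ANOVA and replaced; if non-return depends on the session-1 response, the label effect could be biased in either direction, by a small amount at the dropout the plan expects

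*Combined protocol and SAP*

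**What the plan says.** All places are in the combined protocol and SAP, section C.5 (Aim 2), unless stated.

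- Participants, Recruitment, and Procedures: "We will continue recruitment until we reach the target sample (248 with complete sessions". The only dropout information is here too. A two-session study of similar design in the same laboratory recruited more than 150 users "in the past 2 years with negligible drop out using comparable incentives". No rate is given.
- Sample Size: "This study will include 248 WP smokers (124 beginners; 124 established) randomized to 4 groups (62 each" by label, and "a total sample size of 240 participants will have at least 80% power to detect small-to-medium size effect" (Cohen's f of 0.2).
- Design and Setting asks for equal numbers at each label and order. Experimental Methods adds: "Session order will be randomly counterbalanced to avoid order effects". The sessions are separated by a 48-hour washout.
- Statistical Analysis: "The primary analysis of each outcome will involve a 4-factor analysis of variance (or covariance) with two within-subject factors", namely label and time. The ANOVA is then extended to a mixed-effects linear model. The stated purpose is adjustment for confounders; missing sessions are not mentioned.

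The text defines no analysis set. It gives no rule for a participant with one session, does not say how a replacement is assigned to label and order, and does not plan to report non-return by label or order.

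**The concern.** The recruitment target and the primary method together point to an analysis of people who attended both sessions. Attending session 2 happens after randomisation, and the label may influence it. Objectives and Hypotheses predicts lower satisfaction and greater intention to quit under the label. Experimental Methods expects some of the label's effect to persist between sessions. The 3-month items ask whether participants avoided or stopped waterpipe smoking because of the labels. A person who sees the label first and decides to stop therefore has a reason not to return to smoke again. A person in the no-label-first order has not yet seen a label when deciding whether to return.

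If losses are made up so that order and label stay balanced among completers, the final counts will look even although the loss was one-sided. The HWL versus no-HWL contrast would then rest on a selected group, and nothing planned would show it.

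**Working it through.** **1. The plan's own figure.** Inputs from Sample Size: f = 0.2, alpha 0.05, correlation 0.5, N = 240. With 8 between-subject cells (2 × 4) and m = 4 measurements, a between-subject effect has noncentrality λ = f²·N·m / (1 + (m − 1)ρ) = 0.04 × 240 × 4 / 2.5 = 15.36. The most demanding case has 7 and 232 degrees of freedom and gives power 0.818 (0.833 at 248). The stated 80% is reproduced on this convention. The plan does not name its convention, and some others fall below 80% (m = 2 with 7 degrees of freedom gives 0.728). The present point does not depend on this.

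**2. Assumed inputs for the bias.** None of these is fixed by the documents.
- True label effect 0.38 SD: the pilot f of 0.19 doubled, which presumes the two-group relation d = 2f.
- Correlation between sessions 0.5, as in Sample Size.
- Between-person SD of the label effect 0.5.
- One value per session with unit variance without the label, no period or carry-over effect, and 248 completers split equally by order.
- Loss only in the label-first order, at 2%, 5% or 10% of that order.

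The effect is coded so that a positive value means the label works.

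**3. Formula for the both-sessions analysis.** Removing the top fraction d of a normal selection variable shifts its standardised mean among those kept by −k, where k = φ(z)/(1 − d) and z is the 1 − d normal quantile. This gives k = 0.0494, 0.1086 and 0.195 at 2%, 5% and 10%. Only one of the two orders is affected, so the shift is halved.
- Selection on the session-1 response: the label-session variance is 0.5 + 0.5 + 0.25 = 1.25, and its covariance with the within-person difference is 0.25 + 0.5 = 0.75. The shift is (0.75/√1.25) × k/2 = 0.017, 0.036 and 0.065. Losing the strongest responses gives 0.363, 0.344 and 0.315. Losing the weakest gives 0.397, 0.416 and 0.445.
- Selection on the unobserved individual effect: the shift is 0.5 × k/2 = 0.012, 0.027 and 0.049, giving 0.368, 0.353 and 0.331.

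**4. Simulation with the same inputs**, adding a likelihood analysis of everyone who starts session 1:

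| Who does not return (label-first order) | Analysis | 2% | 5% | 10% |
|---|---|---|---|---|
| Strongest session-1 response | both sessions only | 0.360 | 0.342 | 0.316 |
| | all starters | 0.378–0.381 | 0.378–0.381 | 0.378–0.381 |
| Largest individual label effect (unobserved) | both sessions only | 0.364 | 0.353 | 0.334 |
| | all starters | 0.372 | 0.370 | 0.362 |
| Weakest session-1 response (for example high exposure) | both sessions only | 0.399 | 0.416 | 0.444 |
| | all starters | about 0.38 | about 0.38 | about 0.38 |
| Unrelated to outcome | either | 0.38 | 0.38 | 0.38 |

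Formula and simulation agree to within 0.004.

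**5. Loss in both orders.** With slightly different inputs (effect 0.40 SD, effect SD 0.4), equal loss in both orders selected on the session-1 value keeps 98–99% of the effect at 5% loss, 98% at 10% and 95% at 20%. With selection on session-1 values, it is the imbalance between orders that does most of the harm.

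**6. Scale.** The variance of a within-person difference is 2 × (1 − 0.5) + 0.25 = 1.25, so the standard error is √(1.25/248) = 0.071. A bias of 0.02 SD is about 0.28 of a standard error; 0.064 SD (0.38 − 0.316) is about 0.9 of one.

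**The case against.** A recruitment target is not an analysis set. Counting completers protects power, and the text nowhere says that one-session participants are excluded. The mixed model that the plan already names could include them. This stands in part: exclusion is the consequence of a classical repeated-measures ANOVA, not a stated rule. But the plan makes the ANOVA primary, introduces the mixed model for another purpose, and offers nothing else for a person with one session.

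A reader might infer that the label effect is biased towards null because label-first participants leave and no-label-first participants do not. The documents do not support that. No text says non-return is commoner after the label or absent in the other order, and the table shows bias in either direction or none, depending on who stays away. A reader might also infer distortion of the four-label comparison; no calculation here supports a size for that.

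The plan expects negligible dropout, the sessions are only 48 hours apart, and eligibility requires willingness to attend. This stands as the main reason to call the point minor. It is weaker than it looks on one count: the dropout experience is cited to a flavour-manipulation study, which did not test something meant to discourage smoking.

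Finally, a likelihood analysis is not a complete cure. If non-return follows the individual label effect, which is not observed in someone with one session, the bias is reduced but not removed (0.362 rather than 0.38 at 10% loss).

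**Conclusion.** The point holds as a conditional one. Followed as written, the plan leaves one-session participants out of the primary analysis and replaces them, and nothing elsewhere in the text corrects this. Whether that biases the label effect, and in which direction, depends on a non-return mechanism the documents do not describe. Under the assumed inputs the bias is about 0.02 SD at 2% label-first loss and about 0.06 SD at 10%, in either direction, and nil if loss is unrelated to outcome. At the dropout the plan expects, it is well below one standard error. The loss rates, the 0.38 SD effect and the effect SD of 0.5 are assumptions.

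In the scenarios simulated, the all-starters analysis was at least as close to the truth as the both-sessions analysis. This is therefore a cheap improvement of minor severity. It is not evidence that the planned estimate will be wrong.

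**What to change.** - Define the primary analysis set as everyone randomised who starts session 1.
- Make the already planned mixed model the primary analysis, fitted to all available sessions, with the same label, time, smoking-frequency and label-group terms.
- Show the completers-only ANOVA as a sensitivity analysis.
- Report non-return by label and by session order, and state how additional recruits are assigned to label and order.

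The target of 248 with complete sessions can stay, and so can the power calculation. If a fraction d of all those randomised do not complete, the number randomised is 248/(1 − d): 254 at 2%, 262 at 5% and 276 at 10%. These lie within the stated accrual of 8–10 a month over 36 months (288 to 360). Those people would be recruited under the present rule anyway, so the change adds no participants or visits. The cost is wording and slightly more analysis work. The limit should be stated with it: the mixed model removes the bias only when non-return depends on observed session-1 data, and otherwise only reduces it.
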